9.2. Vital Sign Measurements

The vital signs, body temperature and pulse oximetry will be collected at scheduled timepoints through the trial. Actual values, changes from baseline and abnormal toxicity grading will be summarized by study treatment group and age group for the priming vaccination period using descriptive statistics. Shift in toxicity grades from baseline will be summarized by visit and treatment group for all participants using the frequency count and percentage of participants in each category.

For re-enrolled subjects and the booster vaccination period, separate summaries will be produced for abnormal vital sign assessments by toxicity grading and age group. All data will be included in data listings.

9.3. Clinical Laboratory Evaluations

Clinical chemistry and hematology will be collected at scheduled timepoints. Actual values, changes from baseline, and abnormal toxicity grading for clinical safety laboratory assessment results will be summarized by study treatment group and age group for the priming vaccination period at each timepoint using descriptive statistics. Abnormal toxicity grading is defined as a toxicity grade equal or greater than Grade 1. Shift in toxicity grades from baseline will be summarized by visit and treatment group for all participants using the frequency count and percentage of participants in each category. Shift table for Neutrophils only will also be presented by visit and treatment group for all participants and by race using the frequency count and percentage of participants in each category.

For re-enrolled subjects and the booster vaccination period, separate summaries will be produced for abnormal chemistry and hematology by toxicity grading and age group. All data will be included in data listings.

9.4. COVID-19 exposure and symptoms

The number and percentage of participants reporting symptoms of potential COVID-19 (Yes/No/missing) from CRF page SARS-CoV-2 or COVID-19 Symptoms Assessment will be summarized by treatment groups for the Safety analysis set. For participants reporting ‘Yes’, all symptoms will also be summarized by frequency.

For participants identified as on-study infection, the number and percentage of participants reporting ‘Yes’ to the question Any Symptom of Confirmed COVID-19 from CRF page Clinical Event of Special Interest will be reported by treatment groups and by each priming vaccination period. All symptoms will also be summarized by frequency.

Incidence of COVID-19 and incidence of asymptomatic infection based on the Adverse Event CRF page will be summarized for the following time periods: after first study vaccine dose to 14 days after first study vaccine dose, between 14 days after first study vaccine dose to 2nd study vaccine dose, and after 2nd study vaccine dose to booster vaccine / early termination prior to Day 208 visit. This will also be summarized for re-enrolled subjects separately.

Incidence of COVID-19 and incidence of asymptomatic infection after booster vaccine to early termination after booster vaccine based on the Adverse Event CRF page will be summarized. For subjects not receiving a booster vaccination, events from Day 208 through early termination will be summarized under the Booster Placebo/No Booster group.

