6.1 Evaluation of Participants With Suspected COVID-19

If a participant experiences any of the following potential symptom of COVID-19 (irrespective of perceived etiology or clinical significance), he or she is instructed to contact the site immediately: fever, chills, cough, shortness of breath or difficulty breathing, fatigue, muscle or body aches, headache, new loss of taste or smell, sore throat, congestion or runny nose, nausea or vomiting, and diarrhea.

If the symptoms are confirmed, an Unscheduled Visit should occur. An exception to this rule is if the potential symptoms of COVID-19 are observed within 7 days following first study vaccine administration. Individuals with COVID-19 diagnosed prior to 7 days after first study vaccination will not be required to attend for an unscheduled visit but will be followed clinically for resolution/stabilization in accordance with local practice.

As shown in [Figure 6-1](#), for all other participants evaluated on the basis of clinical symptoms or risk of exposure as assessed at least 7 days after first vaccination, the Unscheduled Visit will be performed at the site (preferred) or via telemedicine visit within 48 hours of symptom onset or identified exposure, and saliva (or nasal swab or nasal turbinate swab) will be collected for testing for SARS-CoV-2 by RT-PCR. Repeat sample collection for SARS-CoV-2 should be performed within 120 hours of onset of symptoms if symptoms persist and the first SARS-CoV-2 test was negative. In addition to the saliva/nasal swab collection, visit procedures will include interview, physical examination, vital signs, pulse oximetry and body temperature measurement, and blood sampling for testing of N antibody to SARS-CoV-2. In the event the visit is performed via telemedicine, the physical examination, vital signs, and blood sampling for testing of N antibody to SARS-CoV-2 will not be required. Participants will be provided with a pulse oximeter, which, along with the previously provided thermometer, will be used to perform daily measurements. **Please note: samples of blood (for binding antibody test for nucleocapsid) and saliva (for RT-PCR testing) sent to the central laboratory are not regarded as diagnostic tests.** Therefore, if clinical suspicion of COVID-19/SARS-CoV-2 exposure exists, local laboratory testing should be performed and/or arrange with a primary care provider as clinically warranted to appropriately manage the care of the participant.

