2.3. Exploratory Objectives and Endpoints

The exploratory objectives and endpoints are presented in Table 2-3.

Table 2-3 Exploratory Objectives and Endpoints

Objective(s)	Endpoint Descriptions
Exploratory	

 To evaluate cell-mediated immune (CMI) responses in participants receiving ARCT-021 versus placebo for priming vaccination 	
CMI responses to SARS-CoV-2 spike antigen may be measured in a subset of participants (CMI subset):
 
 Cytokine-producing SARS CoV-2 Spike protein-specific T-cells 
 as measured by flow cytometry and intracellular cytokine (Tumor necrosis factor (TNF) α, Interleukin-2 (IL-2), Interferon-γ (IFN- γ), IL-4, and IL-13) staining assay at all time points

 To evaluate safety, reactogenicity, and immunogenicity responses in participants receiving ARCT-021, ARCT-154, ARCT-165 versus placebo as booster vaccination given 6 months after priming vaccination 	
Safety:
 
 Any unsolicited AE initiating within 28 days after booster dose of study vaccine administration, by severity and relationship to study vaccine (ARCT- 021, ARCT-154, ARCT-165, or placebo) Any MAAE, NOCD, AE leading to discontinuation/withdrawal or SAE through Early Termination Safety laboratory assessment prior to and 7 days after booster vaccine administration by toxicity grade 
Reactogenicity:
 
 Any solicited local or systemic AE initiating within 7 days after booster vaccine administration, by toxicity grade 
Immunogenicity:
 
 Binding and neutralizing antibody responses (GMFR, SC, GMC, GMT, NAbs/BAbs ratio) before and after booster administration CMI responses before and after booster administration (CMI subset)

 To evaluate the incidence of confirmed COVID-19 in participants vaccinated with ARCT-021, ARCT-154, ARCT-165 versus placebo 	
Confirmed COVID-19 will be assessed in all participants starting 7 days after first study vaccine (ARCT-021, ARCT-154, ARCT-165, or placebo) administration and will include:
 
 Confirmation of COVID-19 symptoms Confirmation of SARS-CoV-2 infection by reverse transcriptase-polymerase chain reaction (RT-PCR) Collection of COVID-19 diagnoses made outside of study-related procedures

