
 To evaluate the incidence of asymptomatic SARS-CoV-2 infection in participants vaccinated with ARCT-021, ARCT-154, ARCT-165 versus placebo 	
Asymptomatic SARS-CoV-2 will be assessed in all participants starting 7 days after first study vaccine and will include:
 
 Confirmation of SARS-CoV-2 infection by RT-PCR Confirmation of seroconversion of SARS-CoV-2 nucleocapsid (N) antibody at timepoints after Day 14

 To assess for vaccine-associated enhanced respiratory disease (VAERD) following vaccination with ARCT 021, ARCT 154, ARCT 165 versus placebo 	
Confirmed COVID-19 cases will be evaluated by an unblinded Data Safety Monitoring Board (DSMB) for frequency and severity in ARCT 021-, ARCT 154-, ARCT 165-, and placebo-vaccinated participants

 To assess the immune responses of ARCT-021, ARCT-154, ARCT-165 compared to placebo using other exploratory assays (eg, plaque reduction neutralizing titer [PRNT], or assays evaluating for responses to SARS-CoV-2 variants) 	
If additional assays and the corresponding blood samples are available, additional immune antibody responses may be evaluated in some or all participants receiving at least 1 administration of study vaccine (ARCT-021, ARCT-154, ARCT-165 or placebo).

3. Investigational Plan

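### SAP 9.4 opens its first infection-incidence window at the first dose, but SAP 2.3 starts both infection endpoints 7 days later, so no row of the incidence table matches the endpoint

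*SAP*

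**What the plan says.** The endpoint definitions are in SAP section 2.3, and Protocol Table 2-3 gives the same start. For symptomatic disease: "Confirmed COVID-19 will be assessed in all participants starting 7 days after first study vaccine". For asymptomatic infection: "Asymptomatic SARS-CoV-2 will be assessed in all participants starting 7 days after first study vaccine". The serological part of the asymptomatic endpoint starts later still: "Confirmation of seroconversion of SARS-CoV-2 nucleocapsid (N) antibody at timepoints after Day 14".

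The analysis is in SAP section 9.4: "Incidence of COVID-19 and incidence of asymptomatic infection based on the Adverse Event CRF page will be summarized for the following time periods". The first period is "after first study vaccine dose to 14 days after first study vaccine dose". The second runs from there to the second dose, and the third from the second dose to the booster or to early termination before Day 208. No Day 7 condition is attached, and the same summary is produced separately for re-enrolled participants.

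SAP Appendix 3 (intercurrent event types) defines study infection as starting on or after Day 7. It treats a positive PCR in the first 7 days as early infection (IcEv4). The paragraph of SAP 9.4 just before the incidence table summarises symptoms among participants with on-study infection, which under Appendix 3 means Day 7 onward.

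On detection, Protocol section 6.1 says: "Individuals with COVID-19 diagnosed prior to 7 days after first study vaccination will not be required to attend for an unscheduled visit".

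**The concern.** The SAP gives two starting points for counting infections and does not reconcile them. The general rule in the SAP introduction, that the SAP prevails over the protocol, cannot settle this because both starting points are in the SAP.

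Two things are at stake. First, a reader who looks to the incidence table for the endpoint of SAP 2.3 will not find it, and cannot rebuild it by adding rows. Second, two neighbouring outputs in SAP 9.4 use different case sets: an infection starting on Day 3 enters the incidence table but not the on-study-infection symptom summary. The first row also pools two stretches of time with different intensity of case finding.

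**Working it through.** No planned sample size, power or error rate bears on this point, so there is no figure of the plan to reproduce. The check is window arithmetic plus a comparison of definitions.

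**Inputs**
- First incidence period: first dose (Day 0) to Day 14 (SAP 9.4).
- Endpoint start: 7 days after the first dose (SAP 2.3; Protocol Table 2-3).
- On-study infection: start date on or after Day 7 (SAP Appendix 3).
- Priming period: up to Day 208 (SAP 4.4).

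**Share of the period that precedes the endpoint** = days before the endpoint start / length of the period
- Continuous time: 7/14 = 50%.
- Whole days, Days 1-14 (Days 1-6 outside): 6/14 = 43%.
- Whole days, Days 0-14 (Days 0-6 outside): 7/15 = 47%.
- Against Day 0 to Day 28: 7/28 = 25%.
- Against the whole priming period: 7/208 = 3.4%.

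**Can the endpoint be rebuilt from the table?** The cut points are the first dose, Day 14, the second dose, and the booster or early termination. Day 7 is not among them. Any sum that includes the first row brings in Days 0-6, and any sum that leaves it out loses Days 7-14.

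**A confirmed infection with onset on Day 3, traced through the SAP**
- Incidence table in 9.4: counted, in the first period.
- Endpoint in 2.3: not counted.
- On-study-infection symptom summary in 9.4: not counted.
- Appendix 3: early infection, if PCR-positive.

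**Detection in the first week**
- Waived or delayed: the symptom-triggered unscheduled visit (Protocol 6.1) and, according to the protocol synopsis, the diary prompts for COVID-19 symptoms and exposure.
- In place: saliva RT-PCR at Day 0 and Day 7 (SAP Appendix 1), a symptom interview at each visit and call (Protocol 6.6), AE collection from consent, and entry of any confirmed case as an AE (SAP 9.1). The AE page is the source that 9.4 uses. Protocol section 6 also describes the diary prompt without a Day 7 start.

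Days 0-6 and Days 7-14 are therefore observed with different intensity, but both are observed.

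**The case against.** The strongest reply is that 9.4 belongs to the safety section. There, data are summarised by period relative to each vaccination, and the safety estimand handles early infection by treatment policy. Counting a Day 3 infection as an event after dose 1 is consistent with that. This stands as a reason to keep reporting the Day 0-6 cases. It does not explain why they share a row with endpoint cases, because the incidence table is also where the incidence objectives of SAP 2.3 are reported.

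A second reply is that 9.4 already has a Day 7 summary, the one on on-study infection, and that all unsolicited AEs are listed by participant. This is true, but that summary describes symptoms, and its case definition is wider than the AE page: Appendix 3 adds nucleocapsid antibody values at or above 5000 AU/mL. It does not replace an endpoint row.

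A third reply is that little depends on the table. The endpoints are exploratory, the protocol calls efficacy assessment not applicable, no hypothesis is tested, and the period is openly labelled. This stands and limits the weight of the point. SAP section 11 does not list the Day 0 start, but Protocol 7.6.5 specifies no windowed incidence analysis, so no planned window was changed.

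A reader might go further and infer three things that the documents do not support:
- **That the first week is unobserved.** The scheduled PCR, interviews and AE recording show otherwise.
- **That early cases were incubating at vaccination and pull a vaccine-to-placebo ratio toward 1.** No passage gives a reason for the 7-day start, and the plan specifies no such ratio. Any figure for the distortion would rest on assumed attack rates.
- **That participants with IcEv4 should leave this table.** Both endpoints are assessed in all participants, and exclusion for IcEv4 belongs to the immunogenicity estimands.

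**Conclusion.** The inconsistency is real and lies within the SAP: section 9.4 counts from the first dose, while section 2.3 and Appendix 3 count from Day 7. The 50% share of the first period is pure calendar arithmetic and assumes nothing about attack rates or vaccine effect. The documents do not allow the number of affected cases to be estimated. The later periods are unaffected, and no primary or secondary conclusion depends on the table. It is best treated as a free improvement that resolves an internal inconsistency, not as a threat to the trial's findings.

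**What to change.** In SAP 9.4, replace the first incidence period with two rows:
- Days 0-6 after the first study vaccine, labelled early infection and marked as outside the endpoint of SAP 2.3.
- Days 7-14 after the first study vaccine, as the first endpoint row.

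Keep both rows in all participants, with no restriction for IcEv4. Leave the second and third periods as they are, and apply the same split to the re-enrolled summary.

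The cost is about one line of SAP text and one extra table row. No data are lost and no new data are needed. The endpoint can then be read from the Day 7-14 row and the two later periods, while the early cases remain visible for safety.

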9.5. Physical Examinations and Emergency Room and/or Hospitalization for COVID-19 Assessment

Listings of complete physical examinations and symptom directed physical examination will be provided. Listings of emergency room visits and/or hospitalization for COVID-19 assessment will be provided.

10. Interim analyses

Three interim analyses will be performed.

- The first interim analysis will focus on safety and will evaluate available safety data for all participants who were initially enrolled as of 05 February 2021 when they have completed Day 7 or Early Termination visit procedures.
- The second interim analysis will evaluate available safety and immunogenicity data for all participants who were initially enrolled as of 05 February 2021 and when they have completed Day 28 or Early Termination visit procedures.

- The third interim analysis will evaluate available safety and immunogenicity data for all participants after they have completed Day 56 or Early Termination visit procedures.

At each of these interim analyses, the datasets from immunogenicity assessments may not contain all participants' data. However, the data cuts outlined above are intended to inform additional clinical development considerations, including selection of ARCT-021 dose for booster administration and selection of final dose and schedule for ARCT-021 administration in the Phase 3 study. The data will be monitored prior to and the database will be locked after the third interim analysis to inform an interim clinical study report.

All available safety and immunogenicity data will be summarized. Blinded data will be shared with the SRC and unblinded data will be shared with the DSMB and sponsor.

Please note that a dry run of safety analysis TLFs will be delivered unblinded to sponsor before the final analysis (i.e., prior to final database lock).

11. Change from Planned Analysis

1. Protocol Section 2.3 states the following exploratory objective: *“To evaluate cell-mediated immune (CMI) responses in participants receiving ARCT-021, ARCT-154, and ARCT-165 versus placebo for priming vaccination”*. This exploratory objective has been revised in SAP section 2.3. to the following: *“To evaluate cell-mediated immune (CMI) responses in participants receiving ARCT 021 versus placebo for priming vaccination.”*
 - Justification: ARCT-154 and 165 are not given as priming vaccinations. This update is to clarify the intent of this exploratory analysis.
2. Protocol Section 7.6.4.2 states the following: *“Seropositivity at a participant level: is defined as a change of NAb titer from below the LOD or Lower Limits of Quantification (LLOQ) to equal to or above LOD or LLOQ (respectively), or a 4-times or higher log-transformed titer ratio in participants with pre-existing NAb titers.”* This definition has been revised in SAP Section 8.2.1 to the following: *“Seropositivity at a participant level is defined as any detectable antibody level above the lower limit of quantification (LLOQ) for the specific assay and antibody measured at timepoints after baseline.”*
 - Justification: Clarify the clinical definition of seropositivity.
3. Protocol Section 7.6.4.2 states the following: *“The common difference of seroconversion rate and 95% CI between each vaccine dose group and the placebo will be estimated using CMH method with stratification factors for each time point from Day 14 to Day 208 for the mITT.”* The Miettinen-Nurminen method will be used instead of the CMH method as stated in SAP Section 8.2.2.2.
 - Justification: CMH uses normal approximation, Miettinen-Nurminen has better coverage property than CMH.

4. Protocol Table 2.3 states that BAbs/NAbs ratio will be summarized. This was revised to have the neutralizing antibodies as the numerator and the binding antibodies as the denominator instead because neutralizing antibodies are a subset of binding antibodies.

12. References

Arcturus Therapeutics, Inc., protocol ARCT-021-04 (A PHASE 2 RANDOMIZED, OBSERVER-BLIND, PLACEBO-CONTROLLED STUDY TO ASSESS THE SAFETY, REACTOGENICITY, AND IMMUNOGENICITY OF THE SARS-CoV-2 VACCINE ARCT-021 IN HEALTHY ADULT PARTICIPANTS) Version 6.0, dated 09 March 2022.

SAS Institute Inc. 2008. SAS/STAT® 9.2 User's Guide. Cary, NC: SAS Institute Inc.

13. Appendices

13.1. Appendix 1: Schedule of Study Procedures

Table 13-1 **Schedule of Events: Priming Vaccinations**

Visit Type (Study Day)	Screen- ing	Dose 1 Adminis- tration	Follow- up 1	Follow- up 2	Study Calls	Dose 2 Administ- ration	Follow- up 3	Follow- up 4	Study Calls	Follow- up 5	Study Calls	Un- sched- uled Visit	Early Termin- ation
		Clinic	Clinic ^a	Clinic ^a	TC	Clinic	Clinic ^a	Clinic ^a	TC	Clinic ^a	TC	Clinic ^a	Clinic ^a
Study Day	-14 to -1	0	7	14	21	28	35	42	49	56	70, 98 ^m , 126 ^m , 156 ^m , 198	n/a	n/a
Procedure Visit Window (in days)	0	0	0	±1	±2	±3	0	±1	±2	±3	±2	n/a	n/a
Informed consent	X												
Inclusion/exclu- sion	X												
Medical history	X												
Weight/Height	X												
Randomization ^b		X											
Physical examination ^c	X	X	X	X		X	X	X		X		X	X
Vital signs, pulse oximetry, and body temperature ^d	X	X	X	X		X	X	X		X		X	X

Visit Type (Study Day)	Screen- ing	Dose 1 Adminis- tration	Follow- up 1	Follow- up 2	Study Calls	Dose 2 Administ- ration	Follow- up 3	Follow- up 4	Study Calls	Follow- up 5	Study Calls	Un- sched- uled Visit	Early Termin- ation
		Clinic	Clinic ^a	Clinic ^a	TC	Clinic	Clinic ^a	Clinic ^a	TC	Clinic ^a	TC	Clinic ^a	Clinic ^a
Pregnancy test ^e	X	X				X							
Urine sampling for drugs/ alcohol	X												
Blood sampling for eligibility ^f	X												
Blood sampling for SARS-CoV-2 antibodies ^g		X		X		X		X		X		X	X
Blood sampling for safety ^f	X	X	X			X	X						
Blood sampling for CMI (CMI subset only) ^h		X		X		X		X		X			X
Saliva sample for SARS-CoV-2 ⁱ		X	X	X		X	X	X		X		X	X
Study vaccine adminstration ^j		X				X							

Visit Type (Study Day)	Screen -ing	Dose 1 Adminis tration	Follow -up 1	Follow -up 2	Study Calls	Dose 2 Administ ration	Follow- up 3	Follow- up 4	Study Calls	Follow- up 5	Study Calls	Un- sched- uled Visit	Early Termin- ation
		Clinic	Clinic ^a	Clinic ^a	TC	Clinic	Clinic ^a	Clinic ^a	TC	Clinic ^a	TC	Clinic ^a	Clinic ^a
Post vaccination observation ^k		X				X							
Adverse Events ¹		X	X	X	X	X	X	X	X	X	X	X	X
Concomitant meds collection	X	X	X	X	X	X	X	X	X	X	X	X	X
Recording of symptoms of COVID 19, and exposure to COVID 19 cases		X	X	X	X	X	X	X	X	X	X	X	X

^aVisits will be performed in person unless the participant is otherwise directed to remain at home or be seen at a hospital. Follow-up visits and unscheduled visits may be performed by telemedicine visits or in a hospital setting if warranted by clinical circumstances (e.g., COVID-19 lockdown in the vicinity) and permitted by local regulation. The target dates for the Day 7 - Day 28 visits are based on the actual date of the Day 0 visit. The target dates for the Day 35-Day 208 visits are based on the actual date of the Day 28 visit. The target dates for visits after Day 208 are based on the actual Day 208 visit.

^bOn Day 0, participants will be randomly assigned to one of four Study Groups (3 ARCT-021:1 placebo), where they will receive 2 doses of study vaccine on Day 0 and Day 28 and also for participants in Study Groups 1, 2, and 3 further randomly assigned to receive a single booster dose of study vaccine (1 ARCT-021:1 placebo) on Day 208. Study Group 4 will not be randomized to receive booster but will receive 1 dose of placebo at Day 208.

^cComplete physical examination will be performed at Screening and Final Visit (Day 570 or Early Termination); symptom-directed examination (if any symptoms) will be performed at other timepoints as indicated to assess changes from Screening.

^dBlood pressure, heart rate, respiratory rate, body temperature, and pulse oximetry will be measured. On days of study vaccine administration, these will be measured before and after vaccine administration.

^ePregnancy testing will be performed on women who are not surgically sterile or postmenopausal. Pregnancy testing by urine dipstick is acceptable. Pregnancy testing will be performed and evaluated prior to study vaccine administration.

^fAnalytes for eligibility and safety assessments are listed in [Appendix 4: Clinical Laboratory Tests](#). Repeat safety laboratory testing at Screening will not be permitted, unless the result is uninterpretable, or Screening assessments are repeated due to lapse of the 14-day screening visit window. On days when study vaccines are administered, blood must be drawn prior to vaccine administration. Throughout the study, additional laboratory analyses may be performed for enrolled participants if relevant to understanding participant safety. The decision to conduct these analyses will be based on discussion between the Medical Monitor and the Investigator and subject to Medical Monitor approval.

^g Immunogenicity samples will include anti-SARS-CoV-2 neutralizing and binding antibodies. On days when study vaccines are administered, blood must be drawn prior to vaccine administration. On unscheduled visits that are performed for assessment of non-COVID-19-related AEs, a blood sample for immunogenicity is not required.

^h At each timepoint blood will be drawn in the participants assigned to the CMI subset. On days when study vaccines are administered, blood must be drawn prior to vaccine administration. Participants assigned to the CMI subset and who re-enroll into the study will not undergo blood sampling for CMI after re-enrollment.

ⁱ Nasal swabs and nasal turbinate swabs may replace saliva testing with alternate means of confirmatory testing of SARS-CoV-2. Participants will receive Home Test Kits if the participant reports possible COVID-19 symptoms or risk of exposure to SARS-CoV-2.

^j Study vaccine will be administered by intramuscular injection into the deltoid muscle of the non-dominant arm. Study vaccine administration will not be performed at these visits if the participant has not met reasons for study vaccine withdrawal.

^k Vaccinated participants will be observed at the site for at least 30 minutes following vaccine administration or until clinically stable.

^l Review of AEs will include surveillance for solicited and unsolicited AEs, SAEs, MAAEs, NOCDs, AEs leading to next vaccine delayed or vaccine will not be re-dosed; data will be gathered by Diary and telephone contacts.

^m At telephone contacts performed from Day 98 through Day 198, participants will be asked if they are interested in re-enrolling into the study to receive ARCT-021 vaccine. Participants eligible to re-enroll to receive ARCT-021 vaccine (placebo group only), will complete the Early Termination visit.

Schedule of Events: Booster Vaccinations

Visit Type (Study Day)	Booster Administration	Booster Follow-up 1	Study Calls	Booster Follow-up 2	Study Calls	Booster Follow-up 3 ^l	Study Calls	Unscheduled Visit	Early Termination	Final Visit
	Clinic	Clinic ^a	TC	Clinic ^a	TC	Clinic ^a	TC	Clinic ^a	Clinic ^a	Clinic ^a
Study Day	208	215	222, 229	236	264, 292, 320, 348, 376	388	416, 444, 472 500, 528, 556	n/a	n/a	570
Procedure/Visit Window (in days)	+60	0	±3	±3	±3	±3	±3	n/a	n/a	+7
Physical examination ^b	X	X		X		X		X	X	X
Vital signs, pulse oximetry, and body temperature ^c	X	X		X		X		X	X	X
Pregnancy test ^d	X									
Blood sampling for safety ^e	X	X								
Blood sampling for SARS-CoV-2 antibodies ^f	X			X		X		X	X	X
Blood sampling for CMI (CMI subset only) ^g	X	X		X		X			X	X
Saliva sample for SARS-CoV-2 ^h	X	X		X		X		X	X	X
Study vaccine administration ⁱ	X									
Post vaccination observation ^j	X									
Adverse Events ^k	X	X	X	X	X	X	X	X	X	X
Concomitant meds collection	X	X	X	X	X	X	X	X	X	X

Visit Type (Study Day)	Booster Administration	Booster Follow-up 1	Study Calls	Booster Follow-up 2	Study Calls	Booster Follow-up 3 ⁱ	Study Calls	Unscheduled Visit	Early Termination	Final Visit
	Clinic	Clinic ^a	TC	Clinic ^a	TC	Clinic ^a	TC	Clinic ^a	Clinic ^a	Clinic ^a
Recording of symptoms of COVID-19, and exposure to COVID-19 cases	X	X	X	X	X	X	X	X	X	X

- ^a Visits will be performed in person unless the participant is otherwise directed to remain at home or be seen at a hospital. The target dates for the Day 215- Day 570 visits are based on the actual date of the Day 208 visit.
- ^b Complete physical examination will be performed at Screening and final visit (Booster Follow-up Visit 3 or Early Termination); symptom-directed examination (if any symptoms) will be performed at other time points as indicated to assess changes from Screening.
- ^c Blood pressure, heart rate, respiratory rate, body temperature, and pulse oximetry will be measured. On days of study vaccine administration, these will be measured before and after vaccine administration.
- ^d Pregnancy testing will be performed on women who are not surgically sterile or postmenopausal. Pregnancy testing by urine dipstick is acceptable. Pregnancy testing will be performed and evaluated prior to study vaccine administration.
- ^e Analytes for safety are listed in [Appendix 2: Clinical Laboratory Tests](#). On days when study vaccines are administered, blood must be drawn prior to vaccine administration. Throughout the study, additional laboratory analyses may be performed for enrolled participants if relevant to understanding participant safety. The decision to conduct these analyses will be based on discussion between the Medical Monitor and the Investigator and subject to Medical Monitor approval.
- ^f Immunogenicity samples will include anti-SARS-CoV-2 neutralizing and binding antibodies and serum samples for exploratory antibody testing. On days when study vaccines are administered, blood must be drawn prior to vaccine administration. See Section [6.3](#) for further detail. On unscheduled visits that are performed for assessment of non-COVID-19-related AEs, a blood sample for immunogenicity is not required.
- ^g At each time point, blood will be drawn in the participants assigned to the CMI subset. On days when study vaccines are administered, blood must be drawn prior to vaccine administration. Participants assigned to the CMI subset and who re-enroll into the study will not undergo blood sampling for CMI after re-enrollment. The CMI assays are described in Section [7.6.5](#).
- ^h Nasal swabs and nasal turbinate swabs may replace saliva testing with alternate means of confirmatory testing of SARS-CoV-2. Participant will receive a Home Test Kit if the participant reports possible COVID-19 symptoms or risk of exposure to SARS-CoV-2.
- ⁱ Study vaccine will be administered by intramuscular injection into the lateral aspect of the deltoid muscle of the non-dominant arm. Study vaccine administration will not be performed at these visits if the participant has not met reasons for study vaccine withdrawal. See Section [4.2.2](#) for further detail.
- ^j Vaccinated participants will be observed at the site for at least 30 minutes following vaccine administration or until clinically stable.

